#### (1) Hepatic toxicity

For patients who developed events related to hepatic toxicity including abnormal hepatic function test values, assess the occurrence status and the differences in patient background, dose, etc. between patients who can be continuously administered this product and patients who must be discontinued administration of this product.

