#### (2) Visual events

Set the presence or absence of visual events as an investigation item. Assess the occurrence status for patients who developed visual events and the differences in patient background, dose, etc. between patients who can be

continuously administered with this product and patients who must be discontinued administration of this product.

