# 7.3.8.1. Confirmation of presence/absence of adverse events that correspond to major investigation items

# 7.3.8.1.1. Presence/absence of hepatic toxicity

The presence/absence of hepatic toxicity including hepatitis, jaundice, hepatic failure, coma hepatic, ALT (GPT) increased, AST (GOT) increased, and GGT increased should be recorded for target patients in this study. If aggravation or new occurrence of hepatic toxicity is observed, the information in detail should be recorded in the adverse event column.

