# 1) Definition of analysis set

The safety analysis set shall include patients for whom the registration in this study and administration of this product have been confirmed and the safety has been evaluated.

The effectiveness analysis set shall include patients for whom the presence/absence of invasive fungal infections has been evaluated among the safety analysis set.

- 2) Analysis method
- (1) Safety analysis

The number of patients who developed each adverse reaction and the proportions will be tabulated. Also, for patients who developed major investigation items of hepatic toxicity and visual events, differences between patients who can continuously receive this product and patients who must discontinue the administration of this product will be analyzed experimentally.

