2.1. Study Design

This study is a prospective multicenter cohort study conducted in patients receiving this product. Pediatric and adult patients who were treated with this product for the purpose of prophylactic administration of this product for invasive fungal infections (IFI) at the commencement of treatment with this product will be included in the study. The observation period shall start on the day of initiation of Vfend treatment and end on the day of completion of treatment; provided that the patients will be followed until the last day of the study period as long as possible if the treatment prolongs. The target sample size is set to be 200 patients in total, 100 patients each for children and adults. The rationale for target sample size is shown below. With hepatic toxicity and visual events considered as major investigation items, tally the occurrence status for patients who developed events related to major investigation items and evaluate the differences in patient background, dose, etc. between patients who can continuously receive treatment with this product and patients who must discontinue treatment with this product.

Rationale for sample size

The sample size is 100 patients each for children and adults, 200 patients in total.

Safety perspectives:

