6. ENDPOINTS AND COVARIATES

6.1. Safety Endpoints

- Adverse drug reactions: Adverse events determined to be related to V fend by the physician
- Adverse events: All-causality adverse events
- Serious adverse events or adverse drug reactions: Adverse events or adverse drug reactions determined to be serious by the physician
- Safety specifications
 - Hepatic toxicity
 - QT prolongation, ventricular tachycardia, ventricular fibrillation, arrhythmia, atrioventricular block complete
 - Visual events
 - Phototoxicity
 - Peripheral neuropathy such as Guillain-Barre syndrome
 - Renal failure
 - Hematologic disorder
 - Interstitial pneumonia
 - Hart failure
 - Consciousnessdistubed
- Major investigation items: Events to be handled as major investigation items among safety specifications are listed below.
 - Hepatic toxicity
 - Visual events
- Laboratory test

White blood cell count, neutrophil count, platelet count, total bilirubin, AST (GOT), ALT (GPT), Al-P, GGT, CRP, BUN, and serum creatinine before the start of treatment with Vfend and by the end date of the observation period in this study

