- Change in treatment with Vfend: If multiple types of change in treatment with Vfend are reported, one of discontinuation, temporarily discontinued, dose reduction, dose increase or no change, in descending order of precedence, will be adopted.
- Outcome: The outcome of the last occurring event will be used.
- Safety specifications

The number and proportion of patients with events will be tabulated. In addition, the number and proportion of patients with safety specifications by change in treatment with Vfend and outcome will be tabulated by SOC and PT.

• Major investigation items

The number and proportion of patients with major investigation items will be tabulated by SOC and PT. In addition, the number and proportion of patients with major investigation items will be tabulated by SOC and PT for each of the following items.

- Change in treatment with Vfend [discontinuation, temporarily discontinued, dose reduction, dose increase, no change]
- Outcome [not recovered, recovered with sequela, recovering, resolved/recovered, unknown]
- Age (1) [<15 years, ≥ 15 years]

Furthermore, in order to examine the difference between patients who discontinued treatment and those who did not by major investigation item, patients with major investigation items will be tabulated by patient background factor, status of discontinuation/completion, concomitant medication, and status of administration.

• Timing of onset of adverse drug reactions

The number of patients with adverse drug reactions will be tabulated by SOC and PT by timing of initial onset of adverse drug reactions. Categories of timing of onset will be every 30 days. However, if there are many adverse drug reactions that occur at an early stage, the analysis will be performed by subdividing the category of the first 30 days as necessary. Major investigation items will be analyzed in the same manner.

For major investigation items, time to event onset will be summarized for each patient in accordance with Section 8.1.4 with the initial onset of the major investigation item considered as an event. Patients without adverse drug reactions will be right-censored after the observation period + follow-up period (28 days) of this study.

• Relationship between concomitant medications and development of adverse drug reactions

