8.2.3.3. Other Endpoints

• Laboratory test values

In patients with hepatic toxicity, an adverse drug reaction considered as a major investigation item, summary statistics of the values of laboratory parameters related to hepatic function (AST, ALT, Al-P, and γ -GTP) at the initiation of treatment, the onset of the adverse drug reaction, and the completion of treatment will be calculated by change in treatment with Vfend. A1.1 Definition of Visit Timing of Appendix 10.1 will be followed for values at the initiation and completion of treatment. The value immediately before the day of onset of adverse drug reaction after the day of initiation of Vfend treatment will be used as the value at onset.

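### The protocol sets the continue-or-stop comparison for hepatic and visual events on adverse events of any cause, while the SAP places it among physician-attributed reactions and plans no all-cause version

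*SAP*

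**What the plan says.** **Protocol.** Section 7.3.8 (1) sets the hepatic comparison thus: "For patients who developed events related to hepatic toxicity including abnormal hepatic function test values". Section 7.3.8 (2) does the same for the eye: "Assess the occurrence status for patients who developed visual events". Section 7.3.8.1, which governs recording, is headed "Confirmation of presence/absence of adverse events that correspond to major investigation items". It covers all target patients and includes ALT, AST and GGT increases. The analysis text in 7.7 plans the comparison "for patients who developed major investigation items of hepatic toxicity and visual events". None of these carries a causality condition.

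**SAP, aims and definitions.** Section 2.1 repeats the aim: "tally the occurrence status for patients who developed events related to major investigation items". Section 6.1 defines adverse drug reactions (ADRs) as "Adverse events determined to be related to V fend by the physician". Separately, it introduces the major investigation items as events.

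**SAP, analyses.** The comparison is in 8.2.3.1, Adverse Drug Reactions: patients with major investigation items are tabulated by background, discontinuation or completion, concomitant medication and administration, "in order to examine the difference between patients who discontinued treatment and those who did not by major investigation item". In the same section, time to first major item censors patients who have no ADR, and the concomitant-medication analysis describes its target as ADRs that count as major items. Section 8.2.3.3 summarises liver tests "In patients with hepatic toxicity, an adverse drug reaction considered as a major investigation item". Section 8.2.3.2 covers all-cause adverse events by SOC and PT and by seriousness only.

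**The concern.** The comparison asks who can stay on the product after an event. A filter on physician attribution may depend on the answer: a physician who stops the product may be more inclined to call the event related, and one who continues through a liver-test rise may be more inclined to call it unrelated. If so, patients who continued are removed more often than patients who stopped, from the table meant to describe both.

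The setting makes this plausible. These are stem-cell transplant patients, and the protocol records GVHD, hepatic disorder, immunosuppressants and interacting drugs (7.3.1, 7.3.3.1), so other explanations for a liver-test rise are often at hand. Protocol 7.9 accepts that, without a control group, judgement of drug-related risk is limited.

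At stake are the share of patients with an event who stop, and the background and dose differences between the two groups.

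**Working it through.** **1. Which population does the SAP use?**

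Pointing to ADRs:
- the heading of 8.2.3.1;
- the censoring rule for time to first major item;
- the closing words of the concomitant-medication analysis;
- the liver-test summary in 8.2.3.3, which is explicit;
- the version 4.0 change note, which describes the added major-item tabulation by age as one of ADRs. That tabulation is in the same block as the comparison.

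Pointing to events of any cause:
- the definition in SAP 6.1 and the aim in SAP 2.1;
- the comparison sentence, which names only patients with major items;
- the safety-specifications item under the same heading, which counts patients with events.

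The ADR reading is likelier, but the text does not settle it.

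**2. The censoring rule needs repair on either reading.** If major items are all-cause, a patient with an unrelated hepatic event and no ADR meets both the event rule and the censoring rule. Taken literally, a patient whose only ADR is neither hepatic nor visual meets neither.

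**3. The plan's own figure.** Protocol 7.5.2 takes N = 200 and incidence 20%, and states at least 31 patients with probability about 95%. Exact binomial: P(X ≥ 31) = 0.957 and P(X ≥ 32) = 0.937. The figure reproduces. Its 20% comes from adverse-reaction rates: 47/233 = 20.2%, 11/45 = 24.4%, 4/21 = 19.0%. So 31 sizes an ADR set.

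Discontinuations among those reactions were 1/47 (2.1%), 2/11 (18.2%) and 2/4 (50%), pooled 5/62 = 8.1% (exact 95% CI 2.7% to 17.8%). At the pooled rate, 31 to 40 ADR patients yield about 2.5 to 3.2 who stop.

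**4. Possible distortion on the ADR reading.** Let d be the true stopping proportion among all patients with the event, and a and b the probabilities of a related call in stoppers and continuers. The tabulated proportion is

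d·a / [d·a + (1 − d)·b].

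All values of d, a and b are assumptions.

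| d | a | b | Tabulated |
|---|---|---|---|
| 25% | 0.9 | 0.5 | 0.225/0.600 = 37.5% |
| 25% | 0.9 | 0.7 | 0.225/0.750 = 30% |
| 25% | 0.8 | 0.8 | 0.200/0.800 = 25% |
| 8.1% | 0.9 | 0.4 | 16.5% |
| 8.1% | 0.5 | 0.5 | 8.1% |

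**5. A background factor can be distorted too.** Take d = 20% with and without GVHD, so no true association, and a = 0.9 in both groups. Let b be 0.25 with GVHD and 0.55 without.
- With GVHD: 0.18/(0.18 + 0.20) = 47%.
- Without GVHD: 0.18/(0.18 + 0.44) = 29%.
- Odds ratio: (0.18/0.20)/(0.18/0.44) = 2.2.

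If GVHD lowers a and b in the same proportion (0.6 and 0.3 against 0.9 and 0.45), the odds ratio is 1.0.

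**6. Size of the all-cause set.** The documents give no all-cause incidence. At an assumed 30%, 40%, 50% or 60%, 200 patients give 60, 80, 100 or 120 expected, and at least 49, 69, 88 or 109 with probability of 95% or more. If related events stay at 20%, the ADR set holds 67%, 50%, 40% or 33% of the patients with hepatic events.

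**The case against.** The best defence is that an ADR analysis is legitimate and no information is destroyed. The objectives concern adverse reactions, 7.7 opens its safety analysis with them, and 7.5.2 sizes the hepatic item on them. Relatedness is a low bar in protocol 9.3 (a reasonable possibility of causing or contributing), and SAP 7 counts causality missing for every dosage form as related. All reported events appear in listings, and SAP 9 lists safety-specification events separately from the ADRs among them.

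Most of this stands, and it is why the ADR tables should stay. It does not answer the point. The low bar and the missing-data rule do not bring back an event recorded as unrelated, and listings are not the comparison that 7.3.8 asks for.

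A reader might go further and infer three things that the documents do not support:
- **That the discontinuation proportion for the 7.5.2 comparison is biased upward.** The earlier figures (1/47, 2/11, 2/4) are themselves discontinuers among adverse reactions, so the ADR subset is the like-for-like set there.
- **That the number of hepatic cases falls below 31.** Both the 20% and the 31 already rest on adverse-reaction rates. Discounting them for attribution would apply the causality filter twice.
- **That selection on the outcome is established.** It depends on an attribution pattern on which the documents are silent, and under equal attribution it vanishes.

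**Conclusion.** The concern holds as a mismatch between protocol and SAP, with a possible but unquantified distortion. The protocol sets the comparison on hepatic and visual events of any cause. The SAP files it under ADRs, treats the items as ADRs in the linked analyses, and plans no all-cause counterpart. It would be too strong to say that the SAP explicitly confines the comparison to related events.

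On the ADR reading, the displacement ranges from none to material: from an assumed 25% to between 30% and 37.5% in the cases shown. The 25% and the attribution probabilities are illustrations, and the cited studies pool to 8.1% among adverse reactions. Only an all-cause table beside the ADR table would let a reader see whether attribution matters. The comparison is descriptive and exploratory (protocol 7.7, SAP 4.1), so no error rate or power is affected.

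**What to change.** In SAP 8.2.3.1 and 8.2.3.3:
- State that the major-item analyses use all hepatic and visual adverse events regardless of causality. This covers incidence, change in treatment, the continue-or-stop tabulation by background and dose, time to onset, and liver tests.
- Show the physician-related subset beside each.
- Reword the time-to-onset censoring so that, in each version, patients without that version's major item are censored.
- Use the related subset for the 7.5.2 comparison with the earlier studies, and say so.

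The cost is SAP wording and a second set of columns. The events and their causality are already recorded (protocol 7.3.7, 7.3.8.1). The drawback is that the all-cause set includes events with other causes, which is why both versions should be shown.

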# [ DOSAGE AND ADMINISTRATION ]

<for Intravenous Use>

Adult	Voriconazole is administered by intravenous drip infusion at the dose of 6 mg/kg twice daily on day 1 and 3 mg/kg or 4 mg/kg twice daily from day 2 onward.
Children (Aged 2 to <12 and 12 ≥ whose body weight is less than 50 kg)	9 mg/kg as voriconazole twice daily on day 1 and 8 mg/kg twice daily from day 2 should be given intravenously. Dose may be increased depending on condition of patients or if poorly responded_by 1 mg/kg at a time, and dose in intolerant patients should be reduced by 1 mg/kg at a time.
Children (Aged ≥12 whose body	6 mg/kg as voriconazole twice daily on day 1 and 4 mg/kg twice
weight is 50 kg or more)	daily from day 2 should be given intravenously.

<tablet></tablet>	
Adult (body weight ≥40 kg)	A recommended oral dose of voriconazole is 300 mg twice daily between meals on day 1, and 150 or 200 mg/dose twice daily between meals on day 2 and thereafter. Dose may be increased depending on condition of the patients or if poorly responded; provided that a total daily dosage should not exceed 400 mg/dose twice daily on day 1 and 300 mg/dose twice daily on day 2 and thereafter.
Adult (body weight <40 kg)	A recommended oral dose of voriconazole is 150 mg twice daily between meals on day 1, and 100 mg/dose twice daily between meals on day 2 and thereafter. Dose may be increased from day 2 onward depending on condition of patients or if poorly responded; provided that a total daily dosage should not exceed 150 mg/dose twice daily.
Children (Aged 2 to <12 and ≥12 whose body weight is less than 50 kg)	After the administration of Voriconazole injection, a recommended maintenance oral dose of voriconazole following injection therapy is 9 mg/kg/dose twice daily between meals. Dose may be increased by 1 mg/kg at a time depending on condition of patients or if poorly responded, and dose in intolerant patients should be reduced by 1 mg/kg at a time (unless the dosage was at its maximum 350 mg, in which case, dose should be reduced by 50 mg at a time). A total daily dosage should not exceed 350 mg/dose twice daily.
Children (Aged ≥12 whose body weight is 50 kg or more)	After the administration of Voriconazole injection, a recommended maintenance oral dose of voriconazole following injection therapy is 200 mg/dose twice daily between meals; which may be increased up to 300 mg/dose twice daily depending on condition of patients or if poorly responded.
<dry syrup=""></dry>	

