#### 7.5.2. Rationale for sample size

It was considered that the following evaluations were possible if the target sample size was set to be 200 patients in total; 100 patients each for children and adults.

Safety perspectives:

In the phase 3 study of prophylactic administration of Vfend in foreign patients with HSCT (study A1501073), the incidence of adverse reactions classified into the SOC of hepatobiliary disorders was 20.2% (47/233 patients). Of those, one patient was led to discontinuation of administration of this product. In the phase 3 study of secondary prophylactic administration of Vfend in foreign patients with HSCT (study A1501038), the incidence of adverse reactions classified into the SOC of hepatobiliary disorders was 24.4% (11/45 patients). Of those, two patients were led to discontinuation of this product. Also, in the clinical study of Vfend conducted in Japanese children (from 2 years old to under 15 years old) (study A1501096), the incidence of adverse reactions related to hepatic toxicity including abnormal hepatic function test values was 19.0% (4/21 patients). Of those, two patients were led to discontinuation of this product. Based on the above, the incidence of hepatic toxicity in patients administered this product for prophylaxis of invasive fungal infections was similar between Japanese and foreign patients and it was considered that such incidence was also similar between adults and children.

In the case where the number of patients to be collected for the special investigation for prophylactic administration of Vfend for invasive fungal infections is set to be 200 patients and the incidence of hepatic toxicity is presumed to be 20%, it is estimated that at least 31 patients with hepatic toxicity will be accumulated at a probability of about 95%. With the cumulation of this sample size, it was considered possible to compare and review the proportion of patients who discontinued the administration of this product with the clinical studies.

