	8.2.2. Patient Background and Treatment History of Vfend						
	- Indication for transplantation was added to patient background.						
	- The presence or absence of concurrent visual disturbance and the breakdown of visual						
	disturbance were deleted because they can be confirmed based on the tabulation of						
	complications by SOC and PT.						
	- The tabulation of hepatic dysfunction and renal dysfunction by disease name was deleted						
	because it is included in the tabulation of complications and overlaps with it.						
	- It was specified to tabulate concomitant medications separately for contraindicated						
	concomitant medications, concomitant medications requiring precautions for						
	coadministration, immunosuppressants, and other antifungal agents.						
	- The tabulation of reasons for discontinuation of prior treatment by drug (antifungal						
	agent) was added.						
	- The tabulation by pregnancy status was added.						
	- The tabulation of administration status by dosage form was deleted, and the tabulation of						
	the initial dose and mean maintenance dose and the tabulation per body weight were						
	added. Furthermore, a subgroup analysis of subjects aged < 15 years and those aged ≥ 15						
	years was added because the doses in children and adults differ.						
	- The analysis of overdose was added.						

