 [absent, present]

In the safety analysis set, the number and proportion of the following patients will be tabulated by System Organ Class (SOC) and Preferred Term (PT) of MedDRA.

- Past medical history
- Concurrent illness
- Concurrent congenital severe immunodeficiency

In the safety analysis set and effectiveness analysis set, the number and proportion of the following patients will be tabulated.

- Contraindicated concomitant medications
- Concomitant medications requiring precautions for coadministration
- Concomitant immunosuppressants
- Concomitantly used other antifungal agents
- Prior treatment (antifungal agents for prophylaxis of invasive fungal infections)
- Reasons for discontinuation of prior treatment (antifungal agents for prophylaxis of invasive fungal infections)
- Presence/absence of pregnancy

In the safety analysis set (women), the number of patients by pregnancy status will be calculated.

• Status of treatment of Vfend

In the safety analysis set, the following status of treatment of Vfend will be tabulated.

- Treatment period [≥1 to <30 days, ≥30 to <60 days, ≥60 to <90 days, ≥90 to <120 days, ≥120 to<150 days, ≥150 to <180 days, ≥180 days]
- Long-term treatment [<180 days, $\geq 180 \text{ days}$]
- Treatment period (days; continuous)
- Dose on the first day (mg; continuous)
- Mean maintenance dose (mg; continuous)
- Dose on the first day (mg/kg; continuous)
- Mean maintenance dose (mg/kg; continuous)
- Overdose³ [absent, present]

The treatment period is from the initial day of administration in this study to the last confirmed day of administration, including the period during which Vfend is suspended.

Tabulation by age (1) [<15 years, \geq 15 years] will be performed in the same manner as above.

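### The dose comparison between patients who stopped and patients who continued after a hepatic event pools all ages, so age mix can appear as a dose difference

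*SAP*

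**What the plan says.** Protocol 7.3.8 makes hepatic toxicity and visual events the major investigation items. For each, it asks how background and dose differ between patients who can stay on the drug and patients who must stop. SAP 2.1 repeats the aim: to "evaluate the differences in patient background, dose, etc. between patients who can continuously receive treatment with this product and patients who must discontinue".

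SAP 8.2.3.1 carries this out as follows: "patients with major investigation items will be tabulated by patient background factor, status of discontinuation/completion, concomitant medication, and status of administration". No stratification by age is named for this comparison. The Age (1) line just above it belongs to the counts of events by SOC and PT.

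SAP 8.2.2 summarises first-day dose and mean maintenance dose, each in mg and in mg/kg, for the safety analysis set, and repeats these tables for patients under 15 and 15 or over. The version 3.0 entry in SAP Section 1 gives the reason: the subgroup analysis at 15 "years was added because the doses in children and adults differ".

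Protocol 7.2.1 gives the labelled doses. By IV infusion, children aged 2 to under 12, or 12 and over and below 50 kg, have "8 mg/kg twice daily from day 2 should be given intravenously", and adults "3 mg/kg or 4 mg/kg twice daily from day 2 onward". Children aged 12 and over weighing 50 kg or more have 4 mg/kg IV from day 2. Oral maintenance is 9 mg/kg per dose for the lighter or younger children, and 150 or 200 mg per dose for adults of 40 kg or more.

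**The concern.** Dose per kg is tied to age by the label, and the planned sample is half children and half adults (Protocol 7.5.1). In a pooled comparison, any difference between children and adults in how often an event leads to stopping is carried over into the dose rows. The table could then suggest that patients who stop had higher (or lower) doses, although dose plays no part within either age group. The SAP takes account of this for the exposure tables, but not for the one comparison in which dose is the question. According to Protocol Section 5, the results feed proper-use information and the re-examination file, so a misleading dose contrast would have readers.

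**Working it through.** **The plan's own figure.** Protocol 7.5.2 expects at least 31 hepatic cases among 200 patients at 20% incidence with probability of about 95%. The binomial tail P(X ≥ 31; n = 200, p = 0.2) is 0.957, so the figure reproduces. The documents give no figure for the dose comparison itself.

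**Inputs.** Hepatic cases: 20% of 100 = 20 children and 20 adults. IV maintenance dose per administration: 8 mg/kg for children, 3 or 4 mg/kg for adults. Every patient is on the labelled dose, so there is no dose effect within age. Stopping rates are assumptions, shown as a range.

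**Formula.** Let s be the share of children in a group. Then

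spurious difference = (s among stopped − s among continued) × (child dose − adult dose).

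**Worked case, 20% of children and 10% of adults stop.** Stopped: 4 children, 2 adults, s = 4/6 = 0.667. Continued: 16 and 18, s = 16/34 = 0.471. Share difference 0.196.
- Adult 4 mg/kg: 0.196 × (8 − 4) = 0.78 mg/kg (6.67 against 5.88).
- Adult 3 mg/kg: 0.196 × (8 − 3) = 0.98 mg/kg (6.33 against 5.35).

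**Other stopping rates.**

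| Children / adults stopping | Share difference | Spurious difference, mg/kg |
|---|---|---|
| 15% / 15% | 0 | 0 |
| 20% / 10% | 0.196 | +0.8 to +1.0 |
| 10% / 20% | −0.196 | −0.8 to −1.0 |
| 50% / 5.2% | 0.561 | +2.2 to +2.8 |

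The last row uses the studies cited in Protocol 7.5.2. In the Japanese paediatric study, hepatic incidence "was 19.0% (4/21 patients). Of those, two patients were led to discontinuation of this product", so 2 of 4 cases stopped. In the two foreign studies, (1 + 2) of (47 + 11) cases stopped, or 3/58 = 5.2%. The exact 95% interval for 2/4 is 7% to 93%.

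**Children on the 4 mg/kg regimen.** If 30% of the child cases were aged 12 or over and 50 kg or more, the mean child dose would be 0.7 × 8 + 0.3 × 4 = 6.8 mg/kg. The 20%/10% result becomes 0.196 × 2.8 = 0.55 to 0.196 × 3.8 = 0.75 mg/kg. The 50%/5.2% result becomes 1.6 to 2.1 mg/kg.

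**Sign in mg.** The documents give no weights; assume adults of 60 kg (180 or 240 mg IV) and a mean child weight w. At 20%/10% the difference is 0.196 × (8w − adult mg):

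| w (kg) | Adult 3 mg/kg | Adult 4 mg/kg |
|---|---|---|
| 15 | −12 mg | −24 mg |
| 20 | −4 mg | −16 mg |
| 25 | +4 mg | −8 mg |
| 30 | +12 mg | 0 mg |
| 40 | +27 mg | +16 mg |

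The mg/kg difference is positive throughout. The sign in mg changes at w = 180/8 = 22.5 kg to 240/8 = 30 kg. For oral doses the change is at 150/9 = 16.7 kg to 200/9 = 22.2 kg. Below those weights the two scales disagree; above them they agree.

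**After a split by age.** In the base scenario the difference is zero in both groups, in mg/kg and in mg. The expected number of hepatic cases is 20 per group, and P(X ≥ 14; n = 100, p = 0.2) = 0.953.

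**The case against.** Several points on the other side carry weight.

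- **The distortion is conditional.** A reader might infer that the pooled dose rows must be biased. They are not if stopping after an event is equally common in children and adults, and the sign reverses if adults stop more often. The only evidence of a difference in the documents is 2 of 4 against 3 of 58. The case definitions differ (hepatobiliary SOC in two studies, hepatic toxicity including test values in the third), and the documents do not state that the foreign studies were in adults.
- **Opposite signs are not general.** A reader might also infer that the mg and mg/kg rows will contradict each other. This depends on child weights that the documents do not give.
- **Not all children are on about twice the adult dose.** Those aged 12 and over and 50 kg or more share an adult IV option.
- **Visual events.** Protocol 7.5.2 expects at least 10 cases and allows that none may discontinue, so there may be nothing to compare.
- **Partly covered already.** Age is among the background factors, so an imbalance would be visible. The SAP does not define status of administration in 8.2.3.1. It may mean the treatment-status block of 8.2.2, which has an age split. The analysis is descriptive (SAP 4.1), further analyses are allowed (SAP 8.2.3.5), and limited control of confounding is acknowledged (Protocol 7.9).

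The first four points limit the size and scope of the concern. The last does not remove it. A marginal age row shows that the mix differs, but not whether dose differs within age, and the 8.2.2 split is written for the whole safety analysis set rather than for event cases by discontinuation status.

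**Conclusion.** The point holds as a cheap improvement. As written, the discontinued-versus-not comparison pools all ages although labelled dose per kg depends strongly on age and weight. Age mix can therefore appear as a dose difference: about 0.8 to 1.0 mg/kg at stopping rates of 20% and 10%, zero at equal rates, and 2.2 to 2.8 mg/kg at the fragile rates of the cited studies. These sizes assume 20 cases per age group, labelled IV doses and no effect of dose within age; they shrink if many child cases have the 4 mg/kg regimen. The mg and mg/kg rows may disagree in sign when the children are light. The documents do not support the stronger readings that the bias is certain or that the two scales always conflict. The practical concern is hepatic toxicity. No labelled dose is questioned here.

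**What to change.** In SAP 8.2.3.1, under major investigation items, add that the dose (status of administration) rows of the discontinued-versus-not tabulation are also shown within Age (1) [<15, ≥15 years], or within the age and weight dosing groups of the label, and that the pooled dose rows are not interpreted alone. The label groups follow dose more closely, because the under-15 stratum can still mix 8 mg/kg and 4 mg/kg patients. Age (1) has the advantage of matching 8.2.2.

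The cost is SAP wording and extra table rows. Dose, dosage form and the weight used for dose calculation are already recorded (Protocol 7.3.2). The price is small cells: at 20% and 10% stopping, about 4 children and 2 adults would have stopped; at the cited rates, about 10 and 1. Individual values may then be more informative than means. Pooling would not cure the sparseness; it would only hide the age mix.
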